4.12 Statistical analysis plan

Feasibility and acceptability of all measures will be assessed by level of completeness and by follow-up qualitative interviews with a sub-sample of participants (see detail above on nested qualitative study). We will calculate recruitment rate via GP surgeries as a percentage of those recruited from those smokers identified on participating GPs lists. We will calculate recruitment via community and online settings as the time taken and spend required to recruit 54 participants and/or the number recruited and spend over three months. We will

calculate the average recruitment rate per day across the three settings. We will provide percentage rates for attrition across each recruitment setting at each of baseline, intervention/control access, and two-month follow-up.

We will look at the observed difference between intervention and control groups for bookings and attendance at SSS and use this data to support estimates for the required sample size for a definitive trial. Clinical significance will also be used in these estimates and a comparison of the two will help to determine future trial feasibility. We will assess level of completeness of all measures and run missing value analysis to determine whether any missing data are missing at random or whether patterns of missing data may indicate a problem with measures.

We will report observed and self-reported bookings, attendances, quit rates set and four-week quits across the intervention and control groups, and the proportion of participants agreeing to allow access to SSS and GP data (where relevant) relating to smoking status and SSS attendance.

We will report on numbers of higher versus lower SES status participants recruited as well as age and gender, and assess using chi-squared analysis whether SES status, age or gender are associated with attrition at baseline, intervention/control access and two-month follow-up.

5. Ethical Considerations

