4.3.3 Online recruitment

The marketing and communications team at Warwickshire County Council (WCC) will be supporting all online recruitment activities. Specifically, they will provide support for online promotion of the study via social media, targeted email marketing, Google advertising and all WCC internal and external channels such as press releases and electronic newsletters. Social media will include Facebook ads as well as via their standard social media channels including twitter feed, Facebook pages and web pages. These ads will appear to anyone in the Warwickshire area searching for health-related products or services. We will run a three-month long campaign to advertise the study. In addition, participating community settings including children's centres, pharmacies and wellbeing hubs will also promote the study online via their communication channels including social media such as Facebook and twitter. Anyone hearing about the study via this method will be able to link directly to the study website.

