4.6 Randomisation

Randomisation will be carried out through the study website during months 10-14 of the study. For this purpose, a digital bespoke randomisation tool (embedded within the study website) will be developed in collaboration with our statistician [name] and with oversight by the Clinical Trials Unit (CTU) at the University of Warwick. This will auto-randomise at the individual level (1:1) using minimisation to ensure balance. Via the study website (hosted by eNgage – see below), the research team will have access to a table that presents live data on condition assignment; NB. the research team will be blind to condition assignment – just condition A and B will be presented. Please see procedure below (section 4.9) for further detail on how and when randomisation occurs.

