4.10 Questionnaire Measures

4.10.1 Baseline measures

A baseline questionnaire will include questions regarding demographic information (including age, gender, profession, ethnicity, postcode (for purposes of identifying indices of multiple deprivation score)) current smoking status, previous use of SSS, ease of internet access, and motivation to guit, measured using the one item 'Motivation to Stop Scale', MTSS (Kotz et al., 2013) and a single item Likert scale (Hummel et al., 2017). Health-related quality of life data will be collected using the EQ5D-5L instrument to inform the health economic analysis, and the ICECAP-A (ICEpop CAPability measure for Adults) instrument will be used to measure general wellbeing. In addition, we have developed a bespoke resource use questionnaire to gain insight into the costs both to individuals and to the public purse of resources accessed as a result of participation in the study or use of the Stopapp (see appendix E). Participants will be given measures online via the project website. If they register but do not complete baseline measures within two weeks we will send email reminders. Those recruited through GP practices will be sent a reminder (using same method as initially used by GP surgery) two weeks after the first communication. All smokers who agree to take part in the study and return baseline guestionnaire responses will be randomised into either the intervention or control group as described above.

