4.11 Estimated recruitment rate and proposed sample size

The primary objective of this study is to assess the feasibility of recruitment to a potential future definitive RCT and therefore formal power analysis is not appropriate. However, in order to determine the target sample size we have drawn on two sources. Teare et al. (2014) recommend that external pilot and feasibility studies with binary outcome measures (in this case attend vs. does not attend SSS) recruit at least 60 participants in each group (minimum N=120) and a maximum of 100 participants in each group (maximum N=200). In addition, our sample size calculations, based on similar definitive RCT data about recruiting smokers to trials via letters from their GPs, suggested that we would need to enrol 980 smokers to detect a 7% difference between control and intervention arms in a definitive trial. Based on this estimate, any trial would need to recruit 1.8 participants per day to achieve the required recruitment in 18 months. We plan to recruit for three months, and based on needing to recruit 1.8 participants per day, we need to reach a required sample size of **162** participants (54 per setting). With a sample size of 162, the recruitment rate of smokers for a full RCT will be estimable with a precision (95% CI width) of +/- 5%.

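### The 1.8-per-day stop/go threshold treats recruitment from four finite GP lists as a constant daily rate over 18 months, and its day count is not fixed

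*Protocol*

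**What the plan says.** Section 4.11 of the protocol starts from the definitive trial: "we would need to enrol 980 smokers to detect a 7% difference between control and intervention arms in a definitive trial". It converts this to a daily rate: "any trial would need to recruit 1.8 participants per day to achieve the required recruitment in 18 months". The feasibility target is that rate applied to a shorter period ("We plan to recruit for three months"), which gives 162 participants, 54 in each of three settings. Section 4.12 will then "calculate the average recruitment rate per day across the three settings". Section 6 names an average of at least 1.8 per day as what would make a future trial feasible. It also says that feasibility turns largely on whether one or more settings can supply the main-trial sample.

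The settings recruit in different ways. In 4.3.1, listed smokers at four practices are invited, one per household. Section 4.10.1 adds one further contact: "Those recruited through GP practices will be sent a reminder (using same method as initially used by GP surgery) two weeks after the first communication". For the online setting, 4.3.3 says: "We will run a three-month long campaign to advertise the study". Section 4.12 also plans measures by setting: GP recruits as a percentage of listed smokers, and for community and online the time and spend to reach 54 and/or the number recruited and spend over three months.

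On timing, 4.6 says: "Randomisation will be carried out through the study website during months 10-14 of the study". Section 4.9.2 places randomisation directly after completion of the baseline questionnaire.

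**The concern.** A daily threshold obtained by dividing 980 by 18 months can be compared with a three-month daily average only if recruitment is roughly constant. The protocol neither states nor checks this.

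It is least plausible for the GP setting. Once the listed smokers at four practices have had their invitation and reminder, no further GP contact is planned. The GP count divided by days therefore depends on how long the lists are and how long the window stays open. What carries over to a larger trial is the yield per listed smoker or per practice. Section 4.12 plans to report that yield, but the threshold in section 6 does not use it. Community and online rates come from a three-month effort, and the protocol does not say whether they will be examined for fading within it.

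Whether the main trial can be done is the study's main question. The threshold could be met without showing that the sources behind it can fill an 18-month trial. Because the day count is not fixed, the same number of recruits could also be read as a pass or a fail.

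**Working it through.** **Inputs.** From 4.11: 980 recruits, 18 months, 1.8 per day, three months, 162 in total, 54 per setting. From 4.3.1: four practices. From 4.6: months 10-14. Months are taken as 30 days, so 18 months = 540 days and three months = 90 days.

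**The plan's own figures.**
- Required rate: 980 / 540 = 1.81 per day, stated as 1.8.
- Feasibility target: 1.8 × 90 = 162.

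Both reproduce, and both steps assume a constant rate. Because 1.8 is rounded, 1.8 × 540 = 972, slightly below 980.

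**Does passing imply 980 in 18 months?** Suppose each setting recruits exactly 54 in 90 days, so that the test is just passed:
- pooled rate: 162 / 90 = 1.8 per day
- each setting: 54 / 90 = 0.6 per day
- community and online together: 1.2 per day, or 1.2 × 540 = 648 in 18 months.

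With community and online continuing unchanged, the 18-month total depends on the GP setting:

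| GP recruitment after month 3 | GP recruits in 18 months | Total | Average per day |
|---|---|---|---|
| Continues in full | 0.6 × 540 = 324 | 972 | 1.80 |
| Half pace | 54 + 0.3 × 450 = 189 | 837 | 1.55 |
| Stops when the four lists are used | 54 | 702 | 1.30 |

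The last row is 702 / 980 = 72% of the requirement.

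**Practices needed to sustain the GP share.** Yield per practice is 54 / 4 = 13.5. The full GP share of 324 then needs 324 / 13.5 = 24 practices, 20 more than the feasibility study mails.

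**Does the section 6 wording on one or more settings remove the problem?** Suppose the GP setting alone gave all 162 from four practices, or 40.5 each. Reaching 980 would still take 980 / 40.5 = about 24 practices, and a daily average would not show this.

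**Effect of the day count.** Months 10-14 is four months elapsed, or five if both end months count.

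| Window | Rate with 162 recruits | Recruits needed for 1.8 per day |
|---|---|---|
| 90 days | 1.80 | 162 |
| 120 days | 1.35 | 216 |
| 150 days | 1.08 | 270 |

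**The case against.** The strongest reply is that the pooled average is not the only measure. Section 4.12 already reports GP recruitment as a percentage of the lists and gives community and online their own metrics, and section 6 speaks of whether one or more settings can supply the main trial. This stands: the information for a sound judgement will largely be collected. But the only numerical threshold does not use it, and section 6 does not say how the two statements combine.

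A reader might infer that the GP rate cannot persist, or that a main trial would stop at 702. The documents do not support that. Section 4.3.1 selects four practices for the feasibility trial only, and nothing limits a definitive trial to them. New practices added in stages could sustain the GP rate. The protocol also does not say that all four practices write at once, so an early burst is an inference.

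A reader might also infer that recruitment is five months long and that 162 recruits would fail at 1.08 per day. Months 10-14 is the randomisation period, and no section makes it the denominator of the recruitment rate. Some lag is natural: people may return later to consent (4.3.2), and incomplete baselines prompt a reminder (4.10.1). Since randomisation follows baseline directly, lag does not obviously account for one or two extra months, and the protocol does not say that it should.

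Finally, projecting from the last month alone would be a debatable choice. With about 36 community and online recruits in that month, the Poisson 95% margin is about 1.96 / √36 = 33%, against 1.96 / √108 = 19% for three months, and a campaign winding down could distort it. That objection is accepted.

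**Conclusion.** The point holds in a limited form. The stop/go threshold and the pooled daily average assume constant recruitment over 18 months, while the GP part comes from finite lists and is not shown to persist. The threshold can be passed at 1.8 per day while the same sources, without new practices, would give about 702 of 980. Keeping the GP share would take about 24 practices, a requirement the criterion leaves out of sight.

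These sizes rest on assumptions: each setting meets exactly 54 in 90 days, community and online continue at the same pace, and each further practice yields 13.5 recruits. The 702 is a scenario that shows what the rule misses, not a forecast.

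Separately, the day count for the rate needs to be stated, and the three months in 4.11 and 4.12 reconciled with months 10-14 in 4.6. This should be corrected because recruitment feasibility is the study's primary objective.

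**What to change.** In 4.12 and section 6, judge feasibility on total recruits projected to 18 months against 980, built up by setting:
- **GP:** the yield per listed smoker already planned in 4.12, multiplied by the listed smokers in the practices realistically available to a definitive trial. State that number of practices.
- **Community and online:** the observed daily rates over the stated window, projected to 18 months, with monthly counts shown as a check for fading. There is no need to project from the final month.

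The pooled daily average can remain as a description. State one recruitment window and its number of days for any per-day rate, and reconcile 4.11 and 4.12 with 4.6, explaining the difference if months 10-14 is meant to allow for late completion of baseline.

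The cost is wording only: under 4.9.2, eNgage already stores each participant's join date and links the ID to the recruitment setting. The downside is that the projection may look less favourable than the pooled average and rests on an assumed number of available practices.

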3.3 Secondary Objectives

Secondary objectives of the feasibility trial are to estimate the:

- **3.3.1** acceptability of randomisation and the StopApp intervention for participants
- **3.3.2** acceptability of primary and secondary outcome measures and measures required for cost-effectiveness and cost utility analyses in a future trial
- **3.3.3** key costs which would be incurred in delivering the intervention and usual care, including a comparison of non-attendance at SSS (Did-not-attend or DNA rates) between each arm of the trial.
- **3.3.4** feasibility of accessing SSS and GP data (if recruited via GP) on attendance, quit dates set and four-week quits for trial participants
- **3.3.5** any differential recruitment and attrition rates across socio-economic groups and age and gender
- **3.3.6** rate of SSS attendance in the treatment and control groups to estimate the event rate of the primary outcome measure for a future trial and support future trial sample size calculations

4. Methodology

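### Section 4.12 uses the observed between-arm difference, which about 81 per arm cannot estimate usefully against a 7-point target, as one input to the definitive sample size and to the feasibility judgement

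*Protocol*

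**What the plan says.** Protocol section 4.12 gives the observed difference two roles. It is an input to sizing: the team will look at "the observed difference between intervention and control groups for bookings and attendance at SSS and use this data to support estimates" of the sample size for a definitive trial. It is also one side of a comparison: "Clinical significance will also be used in these estimates and a comparison of the two will help to determine future trial feasibility". No confidence interval or precision is attached to the difference, and nothing says which source prevails if the two disagree.

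Section 4.11 sizes the feasibility trial on recruitment pace and says that a formal power analysis is not appropriate. It does cite a definitive-trial calculation: "we would need to enrol 980 smokers to detect a 7% difference between control and intervention arms in a definitive trial". The only precision it states, ±5%, concerns the recruitment rate.

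Objective 3.3.6 asks for the "rate of SSS attendance in the treatment and control groups to estimate the event rate of the primary outcome measure for a future trial" and adds that this should support future sample size calculations. It asks for rates in both arms, not for an effect estimate.

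The stop/go criteria in section 6 rest largely on whether the settings can recruit at least 1.8 participants per day on average. They contain no rule based on effect size.

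**The concern.** A trial sized on recruitment pace says little about a between-arm difference of the size expected here. If that difference feeds the definitive calculation, chance feeds it too. A low observed value pulls the calculation towards a very large trial, or makes the intervention look short of clinical significance. A high value pulls the calculation towards a trial too small for the true effect. Because no interval is planned for the difference, a reader of the results would not see how little weight it can bear. At stake are the size of the next trial and part of the judgement on whether to run it.

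**Working it through.** **Inputs from the protocol**
- Section 4.11: 980 smokers for a 7% difference, read here as 7 percentage points of attendance.
- Section 4.11: "any trial would need to recruit 1.8 participants per day to achieve the required recruitment in 18 months".
- Section 4.11: "We plan to recruit for three months".
- Section 4.11: "we need to reach a required sample size of 162 participants (54 per setting".
- Section 4.6: "This will auto-randomise at the individual level (1:1) using minimisation to ensure balance".

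**Reproducing the plan's figures.** 980 / (18 × 30.44 days) = 1.79 per day, which rounds to 1.8. Then 1.8 × 90 days = 162, and 162 / 2 = 81 per arm. The 980 has no unique check, because its control rate, power, significance level and dropout are not stated. At two-sided 5% with no dropout and no continuity correction, it fits a control rate of about 15–16% at 80% power or about 9–10% at 90% power. Allowing 10–20% dropout or a continuity correction widens the range to about 6–16%. An assumed control range of 5% to 20% covers this.

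**Precision of the difference.** With control rate p, intervention rate q = p + 0.07 and n = 81 per arm:

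SE = √{[p(1−p) + q(1−q)] / n}; 95% half-width = 1.96 × SE.

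For p = 0.10: SE = √[(0.0900 + 0.1411) / 81] = 0.0534, and 1.96 × 0.0534 = 0.105.

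The chance columns are exact. They sum the product of the two binomial distributions (81 per arm) over the outcomes concerned, with a true difference of 7 points.

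| Control rate (assumed) | SE, points | 95% half-width, points | Chance observed difference ≤ 0 | Chance < 3.5 points | Chance ≥ 14 points |
|---|---|---|---|---|---|
| 5% | 4.3 | 8.5 | 7% | 18% | 5% |
| 10% | 5.3 | 10.5 | 11% | 23% | 9% |
| 15% | 6.1 | 11.9 | 15% | 26% | 12% |
| 20% | 6.6 | 13.0 | 17% | 28% | 14% |

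The half-width exceeds 7 points once the control rate reaches about 2.2%. The full width exceeds 7 points at every rate tried (12.6 points even at 1%).

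**Fewer participants with outcome data.** Section 5.2 makes consent to record access optional. With 65 per arm and a 10% control rate, the half-width is 11.7 points.

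**How strongly sizing depends on the difference.** This illustrates the limiting case in which the raw difference d is entered alone. It uses n per arm = (z₀.₉₇₅ + z_power)² × [p(1−p) + q(1−q)] / d², with q = p + d and p = 0.10.

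| Difference entered | n per arm, 90% power | n per arm, 80% power |
|---|---|---|
| 3.5 points | 1,774 | 1,325 |
| 7 points | 496 | 371 |
| 14 points | 146 | 110 |

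**What the feasibility data can support.** Suppose, for illustration, that 8 of 81 control participants attend. The rate is 9.9%, with an exact (Clopper–Pearson) 95% interval of 4.4% to 18.5%. Keep the target at 7 points and use 90% power, so that (1.960 + 1.282)² = 10.51:
- Control 4.4%: 10.51 × (0.0421 + 0.1010) / 0.0049 ≈ 307 per arm.
- Control 18.5%: 10.51 × (0.1508 + 0.1900) / 0.0049 ≈ 731 per arm.

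That range is wide too, but it reflects uncertainty in an event rate, which the study is meant to estimate.

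**The case against.** The wording in 4.12 is soft. The data support the estimates, clinical significance is used as well, and the comparison only helps to determine feasibility. Section 6 puts the main weight on recruitment. All of this stands, and it rules out two stronger readings.

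A reader might infer that a chance low difference would end development. The documents do not support that: section 6 has no effect-size stop rule, and its threshold is 1.8 recruits per day.

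A reader might also infer that the definitive sample size would swing twelve-fold (146 to 1,774 per arm). That would require the raw difference to be entered alone, which the protocol does not say. The two ends are also minority outcomes: at a 10% control rate, an observed difference below 3.5 points has a 23% chance and one of 14 points or more a 9% chance.

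Two further limits apply. Objective 3.3.6 asks for rates in both arms to support sample size calculations, so a remedy that kept only the control arm would contradict it. And the protocol never calls 7 points clinically important. It gives 7% only as the difference that 980 smokers would detect.

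The case for leaving the text alone still fails. An estimate this imprecise is named for sizing and for judging feasibility. Adding clinical significance does not cure that, since no rule says how the two combine. A separate analysis plan might settle how they combine, but the choice to use the observed difference is already made in the protocol.

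**Conclusion.** The point holds as a change that should be made. Section 4.12 relies, in part, on an observed difference with a 95% interval of ±8.5 to ±13.0 points when the definitive target is 7 points. It would be zero or negative by chance about 7% to 17% of the time even if the true difference were 7 points. It could therefore mislead the sizing and the feasibility judgement, without being the sole driver of either.

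The figures assume 81 per arm with complete outcome data, a true difference of 7 percentage points, and a control rate between 5% and 20%, which the protocol does not give. Missing outcomes would widen the interval. Reading 7% as a relative difference would make the interval wider still against the target. Using observed event rates for planning, as 3.3.6 sets out, is sound and is not in question.

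**What to change.** In section 4.12:
- Report the between-arm differences in bookings and attendance descriptively, with 95% confidence intervals. State that they will not serve as the target effect or as a feasibility criterion.
- Base the target on a justified minimum important difference. Either justify the 7% used in 4.11 on that ground or agree another value, for example with the service commissioner.
- Keep reporting attendance rates in both arms, as 3.3.6 requires. Recalculate the definitive sample size over the 95% interval of the control-arm rate, with the observed attrition and record completeness.

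The cost is a small wording change in 4.12, with a check that 3.3.6 stays consistent with it. No extra data, participants or resources are needed.

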We will receive data for each of our participants who consented from PharmOutcomes and Outcomes4Health on whether or not they booked an appointment, whether or not they attended an appointment, whether or not they set a quit date and whether or not they achieved a 4 week quit including whether or not this was CO verified. The stop smoking service data will be sent to a secure NHS.net email address held by one member of the research team, in report format, and will include only trial participants who consented to the research team being sent information about their SSS use. This data will be recorded by hand by a researcher directly into a spreadsheet alongside each participant's unique ID generated by eNgage. Each participant's name will be used to link the data (unique ID and stop smoking data) but will not be recorded within the database. Coventry University is currently developing a data sharing agreement with Warwickshire Public Health and Pinnacle Health for this purpose. Recruitment will not begin until this (as well as all other ethics and governance approvals) is in place.

A drop-down box within the Pharmoutcomes/Outcomes4Health appointment data input form used by SSS staff, will include a compulsory prompt to staff to ask whether their client is taking part in the MyWay research project/study (with details of the trial to help recall). If the client answers yes, they will be asked if they agree (consent) to the researcher's contacting the service to collect information about their use of the service, with a 'YES/NO' drop-down box. This acts as a proof of participant consent for Pinnacle health, in order to generate a report of trial participants who provide consent only.

Downloaded data - on completion of data collection, the following will occur:

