4.10.2 Two month follow-up

Follow up emails will be sent approximately two months after completion of the baseline questionnaire, to invite participation in the follow-up questionnaire. Emails containing a link to the follow-up measures will be sent to all participants to assess feasibility and acceptability of these, and likely attrition rates in a future trial. The questionnaire will also ask them to confirm whether they booked an appointment and attended a SSS, set a quit date and reached a 4-week abstinence, and explain what prompted them to book an appointment. Pinnacle Health Ltd will run a search of the PharmOutcomes and Outcomes4Health systems for our participants (where they consented to this) and provide us with their service use data to test feasibility of sourcing objective evidence of booking, attendance (and did not attends; DNAs), guit dates set, and CO tested 4 week guits. We will also assess feasibility and acceptability of follow-up measures of; motivation using the MTSS and a single item Likert scale (Hummel et al., 2017); the EQ5D-5L instrument; the ICECAP-A instrument and a resource use questionnaire to capture participant use of NHS and other resources for both intervention and control arms. Non-responders to the email will be contacted two weeks later with a reminder to respond. We will send an email with a link to the information leaflet provided to the control group, to anyone who contacts us after the end of the period of recruitment to the study until the end of December 2019.

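### Missing value analysis cannot determine that data are missing at random, so a null result could be misread as showing that questionnaire loss is unrelated to attendance or quitting

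*Protocol*

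**What the plan says.** Section 4.12 commits the team to assess the completeness of all measures and to "run missing value analysis to determine whether any missing data are missing at random", and the sentence continues "or whether patterns of missing data may indicate a problem with measures". The same section will "assess using chi-squared analysis whether SES status, age or gender are associated with attrition at baseline, intervention/control access and two-month follow-up".

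On outcomes, section 4.12 will take the difference between groups in bookings and attendance and "use this data to support estimates for the required sample size for a definitive trial". It then adds: "We will report observed and self-reported bookings, attendances, quit rates set and four-week quits across the intervention and control groups".

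There are two sources for these outcomes. One is the emailed two-month questionnaire. The other is the service record system, whose owner will search for consenting participants and "provide us with their service use data to test feasibility of sourcing objective evidence of booking, attendance" (section 4.10.2). Section 4.9.2 limits that source: the report "will include only trial participants who consented to the research team being sent information about their SSS use". Section 5.2 makes consent to record access optional.

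**The concern.** Missing at random means that, given what was observed, the chance of a value being missing does not depend on the value itself. Testing that needs the missing values. A missing value analysis compares missingness with observed variables. An association is evidence against missing completely at random, but it is fully compatible with missing at random. Finding no association does not establish missing at random either. The stated analysis therefore cannot deliver the stated conclusion.

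At stake are the self-reported rates of booking, attendance, quit dates and four-week quits. If people who attended or quit are more (or less) ready to return the questionnaire, the rates among responders are biased while the check shows nothing unusual. Objective 3.3.6 passes an attendance rate on to the definitive trial. That estimate is affected only to the extent that it draws on self-report.

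**Working it through.** **1. What the sentence can and cannot yield.** The plan states no figure here, so there is none to reproduce. The tests named in section 4.12 relate attrition to SES, age and gender. Attendance is not among the listed factors. These tests can reject missing completely at random. They are silent on whether non-response depends on attendance once those factors are taken into account.

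**2. Illustration: inputs.** From the protocol: 162 participants and a 7-point difference (section 4.11), and 1:1 allocation (section 4.6), taken as 81 per arm. Assumed, because the documents give no values: true control attendance *p* of 5%, 10% or 20%, the intervention arm 7 points higher, and response rates *a* in attenders and *n* in non-attenders.

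**3. Rate among responders** = *p·a* / (*p·a* + (1 − *p*)·*n*). Base case, *a* = 80%, *n* = 60%, true rates 10% v 17%:

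- Control: 0.10 × 0.80 / (0.080 + 0.90 × 0.60) = 0.080 / 0.620 = 12.9%.
- Intervention: 0.17 × 0.80 / (0.136 + 0.83 × 0.60) = 0.136 / 0.634 = 21.5%.
- Difference: 8.5 points before rounding, against a true 7.

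Difference among responders, in points, over the range (true difference 7 throughout):

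| Response, attenders / non-attenders | True 5% v 12% | True 10% v 17% | True 20% v 27% |
|---|---|---|---|
| 70% / 60% | 7.9 | 7.8 | 7.6 |
| 80% / 60% | 8.8 | 8.5 | 8.0 |
| 90% / 50% | 11.1 | 10.3 | 8.9 |
| 60% / 80% | 5.5 | 5.6 | 5.9 |

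The range is 5.5 to 11.1, and the sign of the bias reverses when attenders reply less often.

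**4. What the planned tests would show.** In 3,000 simulated trials of the base case, gender, SES and age were set to be unrelated to attendance and response. The chi-squared test rejected in 5.4% of runs for gender and 4.7% for SES. At least one of the three rejected in 13.8%, where chance alone gives 1 − 0.95³ = 14.3%. Response by arm was 62.0% v 63.4%, which a test would detect with about 4% power. The null results follow from the way the example is built. They show that the mechanism is possible, not that it is likely.

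**5. If self-report alone set the next sample size.** Total = 2 × (1.96 + 1.2816)² × [*p*₁(1 − *p*₁) + *p*₂(1 − *p*₂)] / (*p*₂ − *p*₁)², with two-sided 5% and 90% power assumed. True rates: 2 × 10.507 × (0.0900 + 0.1411) / 0.0049 = 991. The base-case responder rates give 808. With response reversed (60% / 80%), responders show 7.7% v 13.3% and the total is 1,239.

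**6. What the records could add.** If records existed for all 162, the base case expects 162 × 0.135 = 21.9 attenders. A comparison of response by recorded attendance would then have about 43% power, and from 10% to over 99% across the table. With records for consenters only, there would be fewer participants to compare. An association would reveal the problem, but a null result would not exclude it.

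**7. Counting non-responders as not attended** gives *p·a*. In the base case this is 8.0% v 13.6%, so this rate and the responder rate lie on either side of the truth in each arm. With response reversed it is 6.0% v 10.2%, and both versions fall below the truth. The pair brackets the true rate only if attenders reply at least as readily as non-attenders.

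**The case against.** - **The sentence is about the quality of the measures.** Read to its end, it serves objective 3.3.2, the acceptability of measures, and no later step uses missing at random to justify a complete-case analysis or imputation. That stands. A reader might infer that a clean result will be used to dismiss attendance-related loss, but the protocol does not say so. The risk is misreading, not a declared use.
- **The sample-size input is largely record-based.** Section 4.12 separates observed from self-reported outcomes, section 4.10.2 treats the records as objective evidence, and section 7 says that the services' systems routinely record the outcome measures. That largely stands. A reader might infer that self-reports feed the future sample size directly, but the documents do not support this. The records do not depend on the questionnaire being returned, but they cover consenters only, so the two sources are not interchangeable.
- **Sensitivity analyses belong in a separate SAP.** Correct, and their absence is no finding. The point rests on a sentence that the protocol does state, and that sentence claims too much.
- **The magnitude assumes its answer.** This also stands. The response rates are invented, and baseline motivation (section 4.10.1) or usage data may carry some signal.
- **The record comparison is harder than it looks.** True. Besides the optional consent at enrolment, section 4.9.2 has service staff ask a second yes/no consent, and the report is generated from that. Someone missing from it may not have attended, may not have been identified as a participant, or may have refused.

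**Conclusion.** The wording is wrong and should be changed: observed data cannot determine that data are missing at random. The consequence is limited. It concerns the self-reported booking, attendance and quit rates, and the event-rate estimate only so far as that relies on self-report. There is no efficacy test to bias, and section 6 rests the decision to proceed largely on recruitment. The documents fix no magnitude. Under the assumed rates a true 7-point difference appears as anything from 5.5 to 11.1 points among responders, and the direction depends on whether attenders or non-attenders reply more. The sample-size totals in the working apply only if self-report alone were carried forward, which the protocol does not state.

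**What to change.** In section 4.12, replace the clause about determining missing at random. Say instead that missingness will be described by arm, setting, SES, age, gender and baseline motivation, and that any association is evidence against missing completely at random only.

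Add one table from the data that section 4.9.2 already links by participant ID: recorded booking and attendance by follow-up response, among participants who gave record-access consent at enrolment. State beneath it that absence from the service report may mean no attendance, non-identification or refusal, and that a null comparison at this sample size does not exclude attendance-related loss.

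Report self-reported event rates both among responders and with non-responders counted as not attended or not quit, noting that the two need not bracket the truth.

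The cost is one reworded clause, one extra table, a second version of the self-reported rates and a less definite statement about missingness. No new data are needed.
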